3. ANALYSIS SETS

3.1. Intent-to-Treat Analysis Set

The intent-to-treat (ITT) analysis set will include all randomized patients.

In the ITT analysis set, treatment will be assigned based on the treatment to which patients were randomized, regardless of which treatment they actually received.

3.2. Modified Intent-to-Treat Analysis Sets

The double-blind modified intent-to-treat (mITT) analysis set is a subset of the ITT analysis set including only patients who receive at least 1 dose of study drug and have at least 10 days of post baseline efficacy assessment on the primary endpoint. The open-label mITT analysis set is a subset of the ITT analysis set including only patients who receive at least 1 dose of study drug during the open-label treatment period and have at least 10 days of post baseline diary entries during the open-label treatment period.

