4.3. Handling Withdrawals and Missing Data

If a patient has ≥ 10 days of electronic headache diary data after 1st dose of the study drug, his/her monthly average number of days/hours of efficacy variables *during the 12-week period* or monthly number of days/hours of efficacy variables *during the 4-week period* will be prorated to 28 days.

Multiple imputation (MI) method will be applied on the primary variable as sensitivity analyses. The methods will be described in detail in Section 6.2.3.

A patient's monthly number of days/hours of efficacy variables *during the 4-week period* after each dose of study drug will be calculated for months 1, 2, and 3. If a patient has missing diary days when calculating the monthly variables, the following method will be used to handle the missing data.

- If a patient has ≥ 10 days of electronic headache diary data for a month, the monthly number of days/hours of efficacy variables will be prorated to 28 days for that month.
- If a patient has < 10 days of electronic headache diary data for a month, the monthly number of days/hours of efficacy variables will be considered as missing.

The weekly number of headache days of at least moderate severity and migraine days will be calculated for the patients' 1st 28 calendar days of diary data after the 1st dose of study drug. Each week is defined as 7 calendar days counted from the 1st dose date. If a patient has missing diary days when calculating the weekly variables, the following method will be used to handle the missing data.

- If the patient has ≥ 3 days of electronic headache diary data for a week, the weekly number of days of efficacy variables will be prorated to 7 days for that week.
- If the patient has < 3 days of electronic headache diary data for a week, the weekly number of days of efficacy variables will be considered as missing for that week.

For the HIT-6 ([Appendix C](#)), if 1 or more items are missing then the total score is missing. The missing questionnaire items handling for the MSQOL questionnaire ([Appendix E](#)) is discussed in [Appendix F](#).

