The **weekly number of days** of efficacy variables (e.g., days of headache with at least moderate severity, migraine days) for each week during the 4-week period after the 1st dose of study drug will be derived and normalized to **7** days equivalent using the following formula.

$$\frac{\sum \text{Days or hours of efficacy variable during the 7 days period}}{\sum \text{Days with assessments recorded in the eDiary for the 7 days period}} \times 7 \quad (6)$$

The mITT analysis sets will be used for all efficacy analyses. Summaries will be presented by treatment group as randomized, unless otherwise noted. For the double-blind treatment period, summaries will be presented for the following treatment groups: placebo, fremanezumab quarterly, and fremanezumab monthly. For the open-label treatment period, summaries will be

presented by migraine classification (ie, CM, EM, and all), double-blind treatment group (ie, placebo, fremanezumab 675 mg/placebo/placebo, fremanezumab 675/225/225 mg, fremanezumab 225/225/225 mg, all fremanezumab), and overall (ie, total). Descriptive statistics for all efficacy data will be presented by month (or week) and over 12-week period for the double-blind period and the open-label period.

The primary and secondary endpoints analysis listed in Section 6.2.1 and Section 6.3 will be repeated for the per-protocol analysis set.

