6.3.1. Electronic Headache Diary Data

6.3.1.1. Definition

The percent reduction in the monthly average number of migraine days during the 12-week period after the 1st dose of fremanezumab will be calculated by formula (4) in Section 6.1. The patient is considered as a responder reaching 50% reduction if his/her percent reduction is 50% or more. If a patient is early discontinued from the study, he/she will be counted as a non-responder.

The percent reduction in the monthly average number of migraine days during the 4-week period after the 1st dose of fremanezumab will be calculated by formula (4) where the postbaseline value will be the number of migraine days prorated to 28 days for month 1. If the patient has 50% reduction or more in month 1, he/she will be considered a responder during the 4-week period after the 1st dose of fremanezumab.

The change from baseline in the monthly average number of headache days of at least moderate severity and the change from baseline in the monthly average number of days of use of any acute headaches medications during the 12-week period after the 1st dose of fremanezumab will be derived similar to the primary efficacy variable using the electronic diary data collected through the corresponding headache diary questions. The baseline values and the postbaseline values will be derived using formula (3) and (1) in Section 6.2.1, and the change is calculated as *postbaseline value – baseline value*.

The change from baseline in the monthly average number of migraine days and the change from baseline in the number of headache days of at least moderate severity during the 4-week period after the 1st dose of fremanezumab will be calculated using formula (2) and (1) in Section 6.2.1, and the change is calculated as *postbaseline value – baseline value*.

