6.3.1.2. Analysis

The change from baseline secondary efficacy endpoints will be analyzed similarly as the primary efficacy endpoint. For the proportion of responders, a logistic regression model will be used with the following effects: treatment, gender, region, special group of treatment failure (Yes or No), and migraine classification (ie, CM or EM). The stratification factors (as randomized) will be used in the model. The odds ratios, 95% CIs for odds ratios, and p-values will be presented for each fremanezumab treatment group (monthly dose and quarterly dose).

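### For the 12-week responder endpoints, the earliest leavers drop out of the denominator while slightly later leavers count as failures, and no analysis of all dosed patients covers the gap

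*SAP*

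**What the plan says.** SAP 6.1 sets the population: "The mITT analysis sets will be used for all efficacy analyses". SAP 3.2 defines the double-blind mITT set as randomised patients who took at least one dose and "have at least 10 days of post baseline efficacy assessment on the primary endpoint". Protocol 9.2.2 and 9.5.4 agree.

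For the 12-week 50% responder endpoint, SAP 6.3.1.1 states: "If a patient is early discontinued from the study, he/she will be counted as a non-responder". SAP 6.4.1.1 repeats that rule for the exploratory 12-week 50%, 75% and 100% responder endpoints.

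The month-1 50% responder endpoint has its own paragraph in SAP 6.3.1.1: "If the patient has 50% reduction or more in month 1, he/she will be considered a responder". That paragraph has no discontinuation rule. Under SAP 4.3, with 10 or more "days of electronic headache diary data for a month, the monthly number of days/hours of efficacy variables will be prorated to 28 days", and a month with fewer than 10 diary days is treated as missing.

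On the model, SAP 6.3.1.2 says: "For the proportion of responders, a logistic regression model will be used with the following effects". The listed effects are treatment, gender, region, treatment-failure group and migraine classification, with stratification factors as randomised.

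SAP 3.1 defines the wider set: "The intent-to-treat (ITT) analysis set will include all randomized patients". Its only planned efficacy use is the imputation analysis, which SAP 4.3 limits to one variable: "Multiple imputation (MI) method will be applied on the primary variable as sensitivity analyses".

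**The concern.** The outcome rule treats leaving early as failure. The analysis set is applied first, however, and removes the patients who leave earliest. Someone who stops after the first injections with 9 diary entries is not analysed. Someone who stops with 10 is a non-responder. Nothing about treatment benefit separates these two patients.

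The 10-day minimum has a purpose for a prorated day count, because a rate needs some days behind it. For a binary outcome that discontinuation fixes as failure, no diary data are needed, and every covariate in the logistic model is known at randomisation.

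The 12-week 50% responder endpoint is the first of six secondary endpoints tested in order under SAP 7. If either dose fails there, the other is tested at 2.5% and testing stops, so the remaining five depend on it. Its denominator depends on events after randomisation, and no planned analysis shows whether that matters. The per-protocol repeat uses a subset of mITT and cannot bring the excluded patients back.

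**Working it through.** **Arm size.** The documents plan no responder rate, so the only figure to reproduce is the sample size (SAP 2.4: difference 1.8 days, SD 6, alpha 0.05, power 90%). A two-sided normal approximation gives 2 × (1.960 + 1.282)² × (6/1.8)² = 233.5, so 234 per arm against 235 stated. Then 235/0.88 = 267.05, so 268 randomised per arm, as stated. I use n = 268 and assume all are dosed.

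**How the rules treat a dosed patient who discontinues early.**

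| Leaves with | 12-week responder | Month-1 responder |
|---|---|---|
| 9 diary days | not analysed | not analysed |
| 10 diary days | non-responder | classified on prorated count |

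The cut-off is 10 of 84 diary days, or 12% of the period.

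A month-1 illustration with assumed values: baseline 14 migraine days, leaves after 10 diary days with 2 migraine days. The prorated count is 2/10 × 28 = 5.6, and the reduction is (14 − 5.6)/14 = 60%. This patient is a month-1 responder and a 12-week non-responder.

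**Effect on one arm.** With r responders and x dosed patients below 10 diary days, the mITT rate is r/(n − x) and the all-dosed rate is r/n. The ratio is n/(n − x), never below 1:
- x = 3: 268/265 = 1.011
- x = 8: 268/260 = 1.031
- x = 33: 268/235 = 1.14 (the extreme in which the whole 12% allowance leaves before 10 diary days)

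**Effect on the contrast.** Rates of 30% (active) and 15% (placebo), and all values of x, are assumptions. The fixed responder counts are 0.30 × 268 = 80.4 and 0.15 × 268 = 40.2. For example, with 8 lost in the active arm only, 80.4/260 − 40.2/268 = 30.9% − 15.0% = 15.9 points.

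| Dropped (active, placebo) | Difference, points | Odds ratio |
|---|---|---|
| 0, 0 | 15.0 | 2.43 |
| 3, 3 | 15.2 | 2.44 |
| 8, 8 | 15.5 | 2.45 |
| 33, 33 | 17.1 | 2.52 |
| 8, 0 | 15.9 | 2.54 |
| 0, 8 | 14.5 | 2.34 |
| 16, 0 | 16.9 | 2.66 |
| 0, 16 | 14.0 | 2.26 |

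Other assumed rates give a similar picture. At 40% vs 20%, 8 to 16 losses in one arm move the 20.0-point difference to between 18.7 and 22.5. At 30% vs 22%, they move the 8.0-point difference to between 6.6 and 9.9.

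For scale, the standard error of the 30% vs 15% difference at 268 per arm is √[(0.30 × 0.70 + 0.15 × 0.85)/268] = 3.5 points. A shift of 0.9 points is about a quarter of that.

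**The case against.** The exclusion is disclosed and reasoned. Protocol 9.3 argues that 10 days give a fair estimate of disease status and that few patients will be lost, and the change log records that text as added at regulators' request. SAP 5.2 will report the size of each analysis set and the withdrawal reasons against an ITT denominator, so the number excluded per arm will be visible. All of this stands. The Protocol 9.3 reasoning concerns estimating a day count, though, and does not address a binary outcome set by rule.

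A reader might infer that the exclusion favours fremanezumab. The documents do not support that. Every arm receives three injections at visit 2, and Protocol 1.2.2.2 reports that adverse events leading to discontinuation in both Phase 3 studies were infrequent and similar across groups. Each arm's own rate can only go up, but the contrast can move either way.

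A reader might also call this a contradiction in the SAP. It is not: an analysis set and an outcome rule applied within it are separate layers, and both can be executed as written. Nor does the asymmetry reach every responder endpoint, because the month-1 paragraph has no non-responder rule for early leavers.

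Finally, the non-responder rule does not supply an outcome for everyone excluded. A patient who stays in the study but makes fewer than 10 diary entries is not covered by it, so the fix has to name that case.

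**Conclusion.** The point holds for the 12-week responder endpoints of the double-blind period: the first secondary endpoint and its exploratory 50%, 75% and 100% relatives. The earliest dosed leavers are removed, slightly later ones are failures, and no ITT or all-dosed responder analysis is planned.

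The likely effect is small. Under the assumed 30% vs 15%, it is 0.2 to 0.5 points if 3 to 8 patients are lost per arm, and about 0.5 to 1.9 points if 8 to 16 are lost in one arm only. The documents give neither the rates nor the counts, and the direction for the treatment difference is unknown. This is worth correcting because the endpoint heads the secondary testing order and the correction is cheap. There is no sign that it would overturn a result.

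The month-1 responder endpoint has a separate gap. An early leaver with 10 or more diary days can be a responder on a prorated count, and an mITT patient with fewer than 10 diary days in month 1 has no defined outcome.

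**What to change.** In SAP 6.3.1.1, 6.3.1.2 and 6.4.1.1, for the double-blind period:

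- Analyse the 12-week responder endpoints on all randomised patients who received at least one dose, by randomised arm.
- Count as a non-responder anyone who discontinues the double-blind period early or has fewer than 10 diary days in it.
- Use the same set for the month-1 50% responder endpoint. Count as non-responders both patients who discontinue during month 1 and patients with fewer than 10 diary days in month 1. Both parts are needed: with the diary rule alone, a leaver with 9 days would be a certain failure and one with 10 could still be a success.
- Keep mITT for the continuous endpoints.

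If the sponsor prefers mITT for the main responder analysis, add the above as a sensitivity analysis at a minimum.

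The cost is a few sentences in three SAP sections. SAP 2.5.2 allows amendments until the first interim database lock. No new data or imputation are needed. Responder rates will be slightly lower, and the few patients who stay in the study with fewer than 10 diary entries will count as failures.

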3.3. Safety Analysis Sets

The double-blind safety analysis set will include all randomized patients who receive at least 1 dose of study drug during the double-blind treatment period. The open-label safety analysis set will include all patients who receive at least 1 dose of study drug during the open-label treatment period.

In the safety analysis sets, treatment will be assigned based on the treatment patients actually received, regardless of the treatment to which they were randomized, unless otherwise specified.

3.4. Per-Protocol Analysis Set

The per-protocol (PP) analysis set is a subset of the double-blind mITT analysis set including only patients who complete the double-blind treatment period without important protocol deviations which may impact the efficacy assessments or any deviations/omissions of the study drug administration. Patients with less than 75% diary compliance during the double-blind treatment period will be excluded from the PP analysis set. Patients who received study drug different from the study drug they were randomized to will be excluded from the PP analysis set. A blinded data review meeting will be conducted prior to the interim database lock in order to determine the exclusion of the patients from the PP analysis set.

4. GENERAL ISSUES FOR DATA ANALYSIS

4.1. General

Descriptive statistics for continuous variables include n, mean, SD, standard error (SE), median, minimum, and maximum. Descriptive statistics for categorical variables include patient counts and percentages, missing category will be displayed as appropriate.

4.2. Specification of Baseline Values

Patients will complete electronic headache diary entries daily for 28-day run-in period and enter headache information (ie, occurrence of headache, duration of headache, maximum severity of headache, and acute migraine-specific medication use) about the previous day into the electronic headache diary device.

If the run-in period is greater or less than 28 days, the baseline values for calculating the change from baseline of the monthly values of the efficacy variables will be normalized to 28 days. The baseline value for calculating change from baseline of the weekly values will be normalized to 7 days.

The efficacy baseline values during the 28-day run-in period derived from the electronic headache diary include

- total headache days of at least moderate severity
- total number of migraine days
- total number of days of use of any acute headache medication
- total headache days of any severity
- total number of headache hours of at least moderate severity
- total number of headache hours of any severity
- total number of days of use of migraine-specific acute headache medications (triptans and ergot compounds) for the group of patients who use migraine-specific acute headache medications at baseline
- total number of days with nausea or vomiting
- total number of days with photophobia and phonophobia

Other efficacy baseline values that will be measured on day 0 before the 1st study drug administration include

- disability score, as measured by the HIT-6
- disability score, as measured by the MIDAS
- quality of life, as measured by the MSQOL questionnaire
- health status, as measured by the EQ-5D-5L questionnaire
- patient depression status, as measured by the PHQ-2 and the PHQ-9

- patient work productivity and activity impairment, as measured by the WPAI questionnaire

Other baseline values will be the last values prior to the 1st dose of study drug.

4.3. Handling Withdrawals and Missing Data

If a patient has ≥ 10 days of electronic headache diary data after 1st dose of the study drug, his/her monthly average number of days/hours of efficacy variables *during the 12-week period* or monthly number of days/hours of efficacy variables *during the 4-week period* will be prorated to 28 days.

Multiple imputation (MI) method will be applied on the primary variable as sensitivity analyses. The methods will be described in detail in Section 6.2.3.

A patient's monthly number of days/hours of efficacy variables *during the 4-week period* after each dose of study drug will be calculated for months 1, 2, and 3. If a patient has missing diary days when calculating the monthly variables, the following method will be used to handle the missing data.

- If a patient has ≥ 10 days of electronic headache diary data for a month, the monthly number of days/hours of efficacy variables will be prorated to 28 days for that month.
- If a patient has < 10 days of electronic headache diary data for a month, the monthly number of days/hours of efficacy variables will be considered as missing.

The weekly number of headache days of at least moderate severity and migraine days will be calculated for the patients' 1st 28 calendar days of diary data after the 1st dose of study drug. Each week is defined as 7 calendar days counted from the 1st dose date. If a patient has missing diary days when calculating the weekly variables, the following method will be used to handle the missing data.

- If the patient has ≥ 3 days of electronic headache diary data for a week, the weekly number of days of efficacy variables will be prorated to 7 days for that week.
- If the patient has < 3 days of electronic headache diary data for a week, the weekly number of days of efficacy variables will be considered as missing for that week.

For the HIT-6 ([Appendix C](#)), if 1 or more items are missing then the total score is missing. The missing questionnaire items handling for the MSQOL questionnaire ([Appendix E](#)) is discussed in [Appendix F](#).

4.4. Study Days and Visits

Study days are numbered relative to the 1st day of study drug administration. The start of treatment (day 1) is defined as the date on which a patient takes the 1st dose of study drug, as recorded on the study drug administration case report form (CRF). Days will be numbered relative to treatment start (ie, ..., -2, -1, 1, 2, ...; with day 1 being the 1st day of study drug administration and day -1 being the day before the 1st day of study drug administration).

The 4-week (28-day) visit windows for the electronic headache diary based efficacy endpoints will be determined based on the actual dosing day. The run-in phase is defined as day -28 to -1

Statistical Analysis Plan

before the 1st injection on day 1. Treatment phase including month 1, 2, 3, 4, 5, and 6 is from the beginning of the 1st injection of study drug to visit 8/day 168 or the end of treatment visit. The 6-month visit windows are separated by each dosing date/time. Month 1 is from the date/time of the 1st dose of study drug administration on day 1 to the date/time just before the 2nd dose. Month 2 is from the date/time of the 2nd dose to the date/time just before the 3rd dose. Month 3 is from the date/time of the 3rd dose to the date/time just before the 4th dose. Month 4 is from the date/time of the 4th dose to the date/time just before the 5th dose. Month 5 is from the date/time of the 5th dose to the date/time just before the 6th dose. Month 6 is from the date/time of the 6th dose to the end of treatment on day 168 approximately.

Throughout this document, all by month efficacy summaries for the headache data will refer to these visit windows.

The weekly (7-day) windows for calculating the weekly efficacy endpoints for the first 28 days will be determined based on the 1st dosing day. The first week is from day 1 to day 7, the second week is from day 8 to day 14, the third week is from day 15 to day 21, and the fourth week is from day 22 to day 28. Only the days between the first and the second dose will be included.

For all other by-visit summaries, if there are multiple assessments at a postbaseline visit then the last non-missing assessment at that visit will be used for the summary. This includes assessments at the scheduled and unscheduled visits.

For patients who withdraw from the study, their safety data at the early termination visit will be excluded from the by-visit summaries but will be included in the last assessment summaries.

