The **monthly average number of days or hours** of efficacy variables (e.g., days of headache with at least moderate severity, migraine days, days of headache with any severity, total hours of headache with any severity, total hours of headache with at least moderate severity, days of use of any acute headache medications, days with nausea or vomiting, days with photophobia and phonophobia etc.) **during the 12-week period** after the 1st dose of study drug will be derived and normalized to **28** days equivalent using the following formula.

$$\frac{\sum \text{Days or hours of efficacy variable over the 12 week period}}{\sum \text{Days with assessments recorded in the eDiary for the 12 week period}} \times 28 \quad (1)$$

The **monthly number of days or hours** of efficacy variables **during a 4-week period** after each dose will be derived and normalized to **28** days equivalent using the following formula, where monthly data separated by each visit of study drug dosing will be used.

$$\frac{\sum \text{Days or hours of efficacy variable during the 4 week period}}{\sum \text{Days with assessments recorded in the eDiary for the 4 week period}} \times 28 \quad (2)$$

The **baseline values** will be calculated using all data collected in the run-in period.

$$\frac{\sum \text{Days or hours of efficacy variable during the run – in period}}{\sum \text{Days with assessments recorded in the eDiary for the run – in period}} \times 28 \quad (3)$$

The **percentage of reduction** in the monthly average number of an efficacy variable will be calculated as

$$\frac{\text{baseline value} - \text{postbaseline value}}{\text{baseline value}} \times 100\% \quad (4)$$

where the baseline value is calculated by formula (3) and the postbaseline value in the equation is calculated by formula (1) for the variables **during the 12-week period** or by formula (2) for the variables **during the 4-week period** after each dose for months 1, 2 and 3.

The **baseline values** for calculating the change from baseline of the weekly number of days of the efficacy variables will use all data collected in the run-in period and be calculated as

$$\frac{\sum \text{Days of efficacy variable during the run – in period}}{\sum \text{Days with assessments recorded in the eDiary for the run – in period}} \times 7 \quad (5)$$

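### SAP 4.4 cuts months 1 to 3 by the number of doses actually given, with no rule for a skipped dose, so a patient who skips a blinded dose and continues can have an open-label month counted as double-blind month 3

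*SAP*

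**What the plan says.** SAP 4.4 ties the diary months to the doses a patient actually receives: "The 6-month visit windows are separated by each dosing date/time". It then defines them one by one, for example "Month 2 is from the date/time of the 2nd dose to the date/time just before the 3rd dose" and "Month 3 is from the date/time of the 3rd dose to the date/time just before the 4th dose". The same section gives these windows a wide scope: "all by month efficacy summaries for the headache data will refer to these visit windows". The treatment phase as a whole "is from the beginning of the 1st injection of study drug to visit 8/day 168 or the end of treatment visit".

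SAP 6.1 uses the months in formula (2), where "monthly data separated by each visit of study drug dosing will be used". Formula (1), which yields the primary endpoint, is separate. It pools diary days over 12 weeks, and the resulting value "after the 1st dose of study drug will be derived and normalized to" a 28-day equivalent. It does not state the first or last day of that period.

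Blinded doses are due at visits 2, 3 and 4. At visits 5, 6 and 7 every patient receives open-label fremanezumab (SAP 2.1). SAP 3.4 foresees skipped doses, since the per-protocol set excludes patients with "any deviations/omissions of the study drug administration". The double-blind mITT set (SAP 3.2) needs only one dose and ten diary days, so these patients remain in the main efficacy analyses.

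**The concern.** The windows count doses, while the blinded phase ends at a visit. The two agree only if nobody skips a blinded dose. For a patient who skips one and carries on, the third dose received is the first open-label dose, and the interval after it becomes month 3 by the stated rule. A placebo patient then supplies a month on active drug as placebo data.

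The affected results are those built from single months: the MMRM (SAP 6.2.3.1), multiple imputation (6.2.3.2), the by-month summaries, and sustained response (6.4.1.1). Imputation gives no protection. It sets a month to missing only when there are fewer than 28 diary days, so a fully recorded open-label month enters as observed.

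Three of the six ordered secondary endpoints use month 1. A skipped visit 3 dose turns their four-week result into an average over about eight weeks, still under blinded treatment.

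The weekly windows in SAP 4.4 are fixed to days 1-28 and limited to days before the second dose. The monthly windows have no comparable limit.

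**Working it through.** **The plan's own figure.** With a difference of 1.8 days, SD 6, two-sided alpha 0.05 and power 90% (SAP 2.4), n = 2 x (1.960 + 1.282)^2 x 6^2 / 1.8^2 = 233.5, so 234 per group. A t-based calculation gives 235 (power 0.9007). Then 235 / 0.88 = 267.05, so 268 per group and 804 in total. The plan's 235, 268 and 804 are reproduced, and nothing below changes them.

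**Windows on nominal days.** SAP 4.4 numbers the first dosing day as day 1. Doses 28 days apart at visits 2 to 7 then fall on days 1, 29, 57, 85, 113 and 141, with open-label drug from day 85. Applying the SAP 4.4 text literally:

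| Blinded dose skipped | Month 1 | Month 2 | Month 3 | Open-label days in month 3 |
|---|---|---|---|---|
| none | 1-28 | 29-56 | 57-84 | 0 of 28 |
| visit 3 | 1-56 | 57-84 | 85-112 | 28 of 28 |
| visit 4 | 1-28 | 29-84 | 85-112 | 28 of 28 |
| visits 3 and 4 | 1-84 | 85-112 | 113-140 | 28 of 28, and all of month 2 |

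After one skipped blinded dose, month 3 is replaced outright. If the visit 5 dose is the one skipped, month 3 stretches to days 57-112 but contains no open-label drug.

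**Reach to a 12-week value.** After one skipped dose, the open-label share is:
- 1/3 for the mean of months 1 to 3, a construction written only for multiple imputation;
- 28/112 = 25% if formula (1) pooled the union of the three windows, which the SAP does not say;
- 0% at nominal timing if formula (1) covers days 1-84.

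**Size.** The documents give no skipped-dose rate. Assume that a fraction f of placebo patients skips one blinded dose and gains the full 1.8 days on open-label drug. The placebo mean then moves toward active by f x 1/3 x 1.8 on the three-month mean and by f x 1.8 on month 3 alone. Power is the normal approximation at 235 per group (0.902 with no dilution), using SD 6 for both measures.

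| f | Three-month mean (days) | Power | Month 3 alone (days) | Power |
|---|---|---|---|---|
| 1% | 0.006 | 0.900 | 0.018 | 0.896 |
| 2% | 0.012 | 0.898 | 0.036 | 0.890 |
| 5% | 0.030 | 0.892 | 0.090 | 0.871 |
| 10% | 0.060 | 0.882 | 0.180 | 0.833 |

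At 1% to 2% of 268 placebo patients, about 3 to 5 people are affected (2.7 to 5.4). The 0.012 days at 2% is 0.012 / 1.8 = 0.7% of the planned difference.

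**Early leavers.** SAP 4.4 closes the treatment phase at the end of treatment visit, and the protocol stops diary entry at the end-of-treatment or early termination visit (footnote to Protocol Table 2). A patient who leaves after one dose therefore has no diary days beyond that visit. No end is written for a month when the next dose never comes. SAP 8.2 sets an end date for patients lost to follow-up (last dose plus 27 days), but for exposure only.

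**The case against.** The best defence is that dose numbers in these documents label scheduled doses. The open-label endpoints are all defined from the fourth dose, which plainly means the visit 5 dose; literal counting would start an affected patient's open-label period at visit 6. SAP 4.4 itself speaks of four-week windows, formula (2) refers to dosing visits, and the MMRM section limits itself to the double-blind period. A careful programmer might never enter open-label days as month 3. This is good evidence of intent. It does not override SAP 4.4, which bases the windows on the actual dosing day and is silent on a visit without a dose. Two programmers could derive different months.

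It is also fair that the case needs a particular patient: one who skips a blinded dose, is not withdrawn for noncompliance (left to the investigator's opinion in Protocol 4.3), and still enters the open-label period. Dropouts alone would explain the SAP 8.2 table of patients with one, two or three doses, so the per-protocol wording is the real sign that omissions are expected.

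Two stronger readings are tempting. A reader might infer that the primary result is contaminated. The documents do not support that: the primary ANCOVA uses formula (1), and no ordered secondary endpoint uses month 3. A reader might also infer that early leavers, planned at 12%, have a window that never closes. They are bounded by the end of treatment visit, where diary entry also stops.

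**Conclusion.** The point holds as a gap in the SAP 4.4 derivation rule, with a small consequence. Taken literally, one skipped blinded dose at visit 3 or 4 makes all 28 nominal days of month 3 open-label, and a skipped visit 3 dose doubles the length of month 1. The open-label days reach sensitivity, descriptive and exploratory results; the month 1 secondary endpoints can be stretched but stay double-blind. For the primary endpoint, the only defect shown is that formula (1) lacks explicit first and last days.

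The expected shift is about 0.01 days on the three-month mean, given two assumptions that the documents do not supply: 2% of placebo patients affected, and a full 1.8-day gain on open-label drug. Even at 10% it is 0.06 days. For placebo patients the bias is toward no difference. Patients in the active arms would also have the wrong month counted, but they are already on active drug and that effect has not been sized. This is a minor point, worth correcting because it is a derivation error at any frequency and cheap to remove.

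**What to change.** Amend SAP 4.4 and the reference to it in 6.1:

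- End each of months 1 to 3 at the next scheduled dosing visit (visits 3, 4 and 5). If that visit or its dose does not occur, use nominal day 29, 57 or 85 as the boundary. Visit anchors alone fail when the visit itself is missed, so the fallback is needed.
- End month 3 and the 12-week period of formula (1) no later than just before the first open-label dose, and state the first and last day of that period. Visit 5 may fall up to 3 days early (Protocol Table 2), so a fixed 84 days without this limit could still admit a few open-label days.
- End an early leaver's last month at the earlier of the end-of-treatment or early termination visit and the nominal month end. State whether the last-dose-plus-27-days rule in SAP 8.2 also applies to diary windows.

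At nominal timing, these windows put 0 open-label days in month 3 for every pattern of skipped blinded doses in the table. The cost is SAP wording and derivation code; sample size, visits and data collection are unchanged. SAP 2.5.2 allows amendments approved before the first interim database lock, so the change can be made before unblinding.
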